Operationally the study will proceed as follows: Subjects will be randomized to one of the three treatment arms. The first interim analysis (toxicity only) will be performed once 18 subjects complete one 28-day cycle.

Subsequent

interim analyses will occur at 13-week intervals to monitor both combined toxicity and disease progression. Depending on the calculated posterior probability of toxicity and disease progression, any one of the three treatment arms may be dropped for excessive toxicity or progression rate.

Safety Analysis

All subjects who receive at least 1 dose of study drug will be included in the safety analyses. AEs, vital sign measurements, clinical laboratory information, and concomitant medications will be tabulated and summarized for each treatment arm during therapy. Subject incidence rates of all AEs (including serious, Grade 3, Grade 4, treatment-related [with and without discontinuation] and events requiring the discontinuation of investigational product), will be tabulated by system class, preferred term, and severity using MedDRA terms and by NCI CTCAE Version 3.0, with modifications recommended by the iwCLL guidelines for the diagnosis and treatment of CLL (Hallek, 2008), and by the Cairo-Bishop grading system for TLS. Time to first dose reduction will be summarized for each regimen.

Death and clinically important AEs (including TFR, TLS, second primary malignancies and thrombosis) will also be summarized.

All other measurements will be summarized using means, standard deviations, medians, minimum, and maximum. Graphical displays will be provided where useful in the interpretation of results.

Efficacy Analysis

Efficacy analyses will be performed on the intent-to-treat (ITT) population that includes all subjects randomized.

Response, duration of response, TTR, TTP, EFS, PFS, and OS will be summarized. The Kaplan-Meier procedure will be used to characterize the time-to-event curves in these analyses when there is censoring.

Exploratory Analysis

Pharmacokinetics Analysis

If the data are sufficient, noncompartmental PK parameters, such as T_{max} , C_{max} , AUC, CL/F, and $t_{1/2}$, will be estimated. Descriptive statistics will be provided for plasma concentrations and PK parameters. Lenalidomide concentration data obtained from all visits may be used to develop the population PK model. The relationship between pharmacokinetics and response (biomarkers or clinical outcomes as appropriate) will be explored.

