8.1.6. Dose and dose interval

Depending on the starting dose, subjects will be allocated in a double-blind fashion to three different regimens and will escalate every 28 days, based on individual subject tolerability, as follows:

- Treatment Arm 1: $5 \text{ mg} \rightarrow 10 \text{ mg} \rightarrow 15 \text{ mg} \rightarrow 20 \text{ mg} \rightarrow 25 \text{ mg/daily}$
- Treatment Arm 2: $10 \text{ mg} \rightarrow 15 \text{ mg} \rightarrow 20 \text{ mg} \rightarrow 25 \text{ mg/daily}$
- Treatment Arm 3: 15 mg \rightarrow 20 mg \rightarrow 25 mg/daily

Toxicities requiring dose interruption and/or modification are described in Section 10.2.3.

The rationale for the dosing for this study is discussed in Section 5.3.3 Rationale for CC-5013-CLL-009 study.

Blinding

To minimize bias for both safety and efficacy parameters based on a subject's treatment regimen, the study was a double-blinded trial. The blind was removed once all patients had completed 3 cycles of treatment.

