15.8. Safety Evaluation

All subjects who receive at least one dose of study drug will be included in the safety analyses.

Adverse events (AE) will be classified using the Medical Dictionary for Regulatory Activities (MedDRA) classification system. The severity of the toxicities will be graded according to the NCI CTCAE version 3.0 whenever possible.

AE frequency will be tabulated by body system, MedDRA preferred term for each treatment regimen during the Treatment Phase as well as for the Follow-up Phase when appropriate. In the by-patient analysis, a subject having the same event more than once will be counted only once. AEs will be summarized by worst NCI CTCAE version 3.0 grade. In the case that the AEs or event frequencies are judged to be clinically important, an exact test may be used to analyze the difference between the treatment groups.

AEs leading to death or to discontinuation from treatment, events classified as NCI CTCAE version 3.0 Grade 3 or higher, study-drug-related events, and serious adverse events (SAEs), and events of interest (including second primary malignancies) will be summarized separately.

Laboratory data will be graded according to NCI CTCAE version 3.0 severity grade. Cross tabulations will be provided to summarize frequencies of abnormalities.

For vital sign and body weight data, means, medians, standard deviations, minimum and maximum values will be provided.

Graphical displays will be provided where useful to assist in the interpretation of results.

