#### **5.1.2. Duration of Treatment**

Subjects will receive study drug until PD or unacceptable toxicity develops. The continuation of lenalidomide treatment duration until disease progression is supported by Chanan-Khan and Ferrajoli studies which report that subjects with relapsed CLL that have received lenalidomide therapy for more than one year continue to improve their response to treatment (Chanan-Khan, 2006a) (Chanan Khan, 2007) (Ferrajoli, 2008). In the Chanan-Khan study the median time to best response was 5.9 months (range 1.6 to 18.3 months). In the Ferrajoli study time to best response was 6 months in 11 subjects and 9 months in 3 subjects.

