## 5.2. Study Endpoints

### Primary

- Safety [type, frequency, and severity of adverse events (AEs) and relationship of AEs to lenalidomide]

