### 12.1. Adverse Events

The adverse events of Neutropenia, Anemia and Thrombocytopenia will be analyzed according to the grading system as recommended by the IWCLL guidelines for the diagnosis and treatment of CLL (Hallek, 2008).

The adverse event of Tumor Lysis Syndrome (TLS) will be analyzed according to the grading system as recommended by Cairo-Bishop grading system.

Treatment emergent adverse events (AEs) will be summarized by treatment arm and overall. A treatment emergent adverse event is defined as any AE occurring or worsening on or after the first treatment of any study drug, and within 30 days after the last dose of the last study drug received. Adverse events will be presented in descending order of frequency (for all subjects) by SOC, and then within each SOC, by decreasing order of preferred term. Adverse events are documented on the CRF together with their severity, according to the NCI CTCAE version 3.0 or higher, also referred to as NCI toxicity grading. For the categorization of the adverse events, the MedDRA® dictionary (version 15.0) will be used.

AE frequency will be tabulated by body system, MedDRA preferred term for each treatment regimen during the Treatment Phase as well as for the Follow-up Phase when appropriate. In the by-subject analysis, a subject having the same event more than once will be counted only once and by the greatest severity. AEs will be summarized by worst NCI CTCAE version 3.0 grade. In the case that the AEs or event frequencies are judged to be clinically important, an exact test may be used to analyze the difference between the treatment arms. Events of interest will also be summarized by treatment cycles.

AEs leading to death or to discontinuation from treatment, events classified as NCI CTCAE version 3.0 Grade 3, 4, and 4 AEs, treatment-related events, serious adverse events (SAEs) and events of interest (including second primary malignancies) will be summarized separately.

Individual AE listings by subject will be provided.

As an exploratory analysis, AEs will be summarized by treatment arm and by subgroup (i.e., relapse vs. refractory, age <65 vs. age ≥65, lines of prior CLL treatment, gender).

Adverse events (AE) will be classified using the Medical Dictionary for Regulatory Activities (MedDRA) classification system. The severity of the toxicities will be graded according to the NCI CTCAE version 3.0 whenever possible.

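### Adverse events are tabulated only as crude per-subject incidence over open-ended time on drug, so unequal treatment duration would distort the arm-by-arm safety tables for events with continuing risk

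*SAP*

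**What the plan says.** Safety, described through the type, frequency, severity and drug relationship of adverse events, is the primary endpoint (Protocol 7.1, SAP 5.2). The Safety Analysis part of the Protocol Synopsis names the measure: "Subject incidence rates of all AEs". Protocol 15.8 gives the counting rule, "a subject having the same event more than once will be counted only once", and SAP 12.1 adds the grade: "a subject having the same event more than once will be counted only once and by the greatest severity".

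SAP 12.1 treats an event as treatment-emergent if it starts or worsens from the first dose onward and "within 30 days after the last dose of the last study drug received". SAP 5.1.2 sets no fixed treatment period: "Subjects will receive study drug until PD or unacceptable toxicity develops". For events judged clinically important, SAP 12.1 says that "an exact test may be used to analyze the difference between the treatment arms"; it gives no significance level or sidedness.

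Three planned items bear on time:
- SAP section 9 derives treatment duration and days on drug and describes them by arm in separate tables.
- The same section plans time to first dose reduction or interruption due to an adverse event.
- SAP 12.1 plans a by-cycle summary, for events of interest only, without stating its denominator.

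In the visible text, days on drug are never the denominator of an adverse event rate. Neither document plans a time-to-first-event analysis, a cumulative incidence or a fixed-window comparison of adverse events.

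**The concern.** A percentage of subjects with an event mixes two things: how fast events occur, and how long subjects were watched. Here each subject's watch ends 30 days after the last dose, so it follows time on drug. If one arm stays on drug longer, it collects more first events of any kind whose risk continues during treatment, even at an identical hazard.

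The error can also run the other way. An arm that stops early because it is toxic has less time to accrue further events, and can look no worse than a better-tolerated arm. In a study whose primary objective is the safety of competing regimens, that is the more serious mistake. The duration tables in SAP section 9 would show an imbalance, but would leave the reader to correct for it by eye.

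**Working it through.** **Figure in the plan.** The adverse event section contains no number to reproduce. The only related figure is the sample size in SAP 6.1: 35 × 3 = 105, which checks.

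**Inputs from the documents.**
- 35 subjects per arm (SAP 6.1).
- Risk window of time on drug plus 30 days (SAP 12.1). At the 30.4 days per month of SAP 6.5.3, w = 30/30.4 = 0.987 months.
- To set the scale only, the predecessor study CLL-001 (Protocol 5.3.2.3): median treatment 3.1 months, with Grade 3/4 infection in 40%, neutropenia in 65% and thrombocytopenia in 33%.

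**Assumptions.**
- The event hazard λ is constant and the same in both arms.
- Time on drug is exponential with median m and independent of the event.
- The longer arm's median is 1.25, 1.5, 2 or 3 times 3.1 months.
- The optional exact test is a two-sided Fisher test at 0.05.

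**Formula.** With μ = ln 2 / m, crude incidence = 1 − exp(−λw) × μ/(μ + λ).

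**Calibration.** At m = 3.1, μ = 0.2236 per month. Setting incidence to 40% gives λ = 0.1105 per month. Check: 1 − 0.8966 × 0.2236/(0.2236 + 0.1105) = 1 − 0.8966 × 0.6692 = 0.400.

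**Worked case, twice the duration.** At m = 6.2, μ = 0.1118. Incidence = 1 − 0.8966 × 0.1118/(0.1118 + 0.1105) = 1 − 0.8966 × 0.5028 = 0.549.

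**Results.** Each cell gives crude incidence in the longer arm and, in brackets, the Fisher rejection probability against the 3.1-month arm, by exact enumeration with 35 per arm. True hazards are equal throughout.

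| Incidence in 3.1-month arm | 1× | 1.25× | 1.5× | 2× | 3× |
|---|---|---|---|---|---|
| 40% | 40.0% (2.8%) | 44.6% (3.8%) | 48.5% (6.6%) | 54.9% (15.7%) | 63.9% (40.3%) |
| 33% | 33.0% (2.9%) | 37.3% (4.1%) | 41.0% (7.0%) | 47.3% (16.4%) | 56.6% (40.4%) |
| 65% | 65.0% (2.9%) | 69.2% (4.0%) | 72.5% (6.6%) | 77.3% (14.2%) | 83.2% (31.7%) |
| 10% (assumed) | 10.0% (1.3%) | 11.8% (1.8%) | 13.5% (2.8%) | 16.8% (6.6%) | 22.7% (20.1%) |

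**Reverse direction.** Give the 3.1-month arm a hazard of 0.1883 per month, which is 1.70 times 0.1105. Its crude incidence is 1 − exp(−0.1883 × 0.987) × 0.2236/(0.2236 + 0.1883) = 1 − 0.8304 × 0.5429 = 0.549. That equals the 6.2-month arm at the lower hazard, so the crude table would show no difference.

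**Check of the remedy.** In a simulation of 2,000,000 subjects per arm with λ = 0.1105, first events per person-month at risk were 0.1105 in the 3.1-month arm and 0.1106 in the 6.2-month arm, a ratio of 1.00. The crude ratio is 0.549/0.400 = 1.37.

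**Where the remedy fails alone.** Confine the hazard to the first month, at 0.4 per month in both arms. Crude incidence is then 33% in both, which is right. The person-month rate is 0.086 in the 3.1-month arm and 0.048 in the 6.2-month arm, which wrongly favours the longer arm.

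**The case against.** The strongest reply is that no confirmatory safety comparison exists to be biased. The tables are descriptive by arm, the exact test is optional, and duration is reported beside them. This stands: the rejection probabilities only gauge how misleading a crude contrast could be. They are not the error rate of a planned primary test.

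Second, the documents show that time on drug is open-ended, not that it differed by arm. This also stands. With equal durations there is no bias, and at 1.25 times it is under 5 points.

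Third, not every event has a continuing hazard. In the CLL-001 data given in the protocol's amendment summary, 4 of 5 tumor lysis cases under the original design and both cases under the amended design began within about 15 days, as did 6 of 7 serious tumor flare cases under the amended design. The 30-day tail covers that period even for early stoppers, so crude incidence serves such events well. A person-month rate does not.

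Fourth, the interim toxicity model is redacted (SAP 6.3 and 14.2), and SAP 13.3 plans regression comparisons of treatments without naming the outcomes. Nothing is concluded here about either.

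A reader might go further and infer that the tables dilute a starting-dose contrast, because Table 4 of the protocol plans 25 mg in every arm from Cycle 5, and because "The blind was removed once all patients had completed 3 cycles of treatment". The documents do not support that. The objective is the safety of whole dose regimens (Protocol 6.1), and Protocol 15.1 makes the escalation schemes themselves the object of study. Escalation also depends on tolerability, so planned convergence need not be actual: in CLL-001, 42% could not go beyond 5 mg. For the same reason the documents do not call for a Cycle 1 to 3 window as the main comparison. It would demote later toxicity, including the second primary malignancies that the protocol follows for years.

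**Conclusion.** The gap is real but limited. In the visible text, the adverse event tables for the primary endpoint ignore time at risk, although treatment length is open-ended and days on drug are already derived. For events with continuing risk and a crude rate of 33% to 65% in the shorter-treated arm, the distortion is about 4 to 5 points at a duration ratio of 1.25 and 12 to 15 points at a ratio of 2. At a ratio of 2, a hazard 1.7 times higher in the arm that stops early could be hidden completely.

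These sizes rest on a constant hazard, on exponential time on drug independent of the event, and on assumed duration ratios. They illustrate the mechanism and do not estimate a bias in this trial. The harm is to the reading of descriptive tables, and it largely spares early events such as tumor lysis and tumor flare. This is a cheap improvement and does not invalidate the planned safety analysis.

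**What to change.** Keep every crude table in SAP 12.1. For Grade 3 or higher events, serious adverse events and events of interest, add by arm:

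1. The rate of first events per person-month at risk, with 95% confidence intervals. Time at risk runs from first dose to the first event or the end of the treatment-emergent window, whichever comes first.
2. The cumulative incidence of the first event over time, with death as a competing event, including an estimate at a fixed early point (for example the end of Cycle 3). Label the early estimate supplementary.

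For the by-cycle summary already planned, state that the denominator is the number of subjects at risk in that cycle.

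The cost is SAP wording and a few more tables. Dosing dates and adverse event onset dates are already used in the SAP, so no new data are needed. One caution belongs in the text: the person-month rate must be read beside the cumulative incidence display, because it misleads when risk is concentrated early in treatment.

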21.4. Grading of Hematological Toxicity (Hallek, 2008)

Grade ^a	Decrease in Platelets ^b or Hb ^c (nadir) From Pretreatment value (%)	Absolute neutrophil count/μL ^d (nadir)		
0	No change to 10%	≥ 2,000		
1	11% - 24%	≥1,500 and < 2,000		
2	25% - 49%	≥1,000 and < 1,500		
3	50% - 74%	≥ 500 and < 1,000		
4	≥ 75%	< 500		

- a.Grades: 1, mild; 2, moderate; 3, severe; 4, life-threatening; 5, fatal. Death occurring as a result of toxicity at any level of decrease from pretreatment will be recorded as grade 5.
- b. Platelet counts must be below normal levels for grades 1-4. If, at any level of decrease the platelet count is $<20,000/\mu\text{L}$, this will be considered grade 4 toxicity, unless a severe or life-threatening decrease in the initial platelet count (e.g., $20,000/\mu\text{L}$) was present pretreatment, in which case the patient is not evaluable for toxicity referable to platelet counts.
- c.Hb levels must be below normal levels for grades 1-4. Baseline and subsequent Hb determinations must be performed before any given transfusions. The use of erythropoietin is irrelevant for the grading of toxicity, but should be documented.
- d. If the absolute neutrophil count (ANC) reaches less than 1,000/μL, it should be judged to be grade 3 toxicity. Other decreases in the white blood cell count, or in circulating granulocytes, are not to be considered, since a decrease in the white blood cell count is a desired therapeutic end point. A gradual decrease in granulocytes is not a reliable index in CLL for stepwise grading of toxicity. If the ANC was less than 1,000/μL prior to therapy, the patient is not evaluable for toxicity referable to the ANC. The use of G-CSF is irrelevant for the grading toxicity, but should be documented.

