## 12.5. Deaths

Deaths during the treatment phase and within 30 days from the last dose of study treatment will be tabulated by the primary cause of death and treatment arms. Separate summary tables will be made for the deaths that are suspected to drug related and for those that are considered non-drug related.

The same summary tables will be provided for the deaths that occur during follow-up phase separately.

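### SAP 12.1 lists the severe-AE summary as Grades 3, 4 and 4, which read literally leaves out the Grade 5 events that protocol 15.8 includes

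*SAP*

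**What the plan says.** SAP 12.1 (Adverse Events) names several AE subsets to be summarized separately. The severe-event subset is worded "events classified as NCI CTCAE version 3.0 Grade 3, 4, and 4 AEs". Protocol 15.8 (Safety Evaluation) has the matching list, and there the subset is "events classified as NCI CTCAE version 3.0 Grade 3 or higher".

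Grade 5 is in use in this trial. The severity scale in protocol appendix 21.1 ends at Grade 5, death. Appendix 21.4, which governs hematological toxicity, says: "Death occurring as a result of toxicity at any level of decrease from pretreatment will be recorded as grade 5". The TLS grading table in appendix 21.3 also runs to Grade 5.

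SAP 12.1 adds a counting rule: a subject who has the same event more than once contributes one count, at the worst severity.

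The SAP also plans other outputs that reach fatal events. In 12.1, "AEs will be summarized by worst NCI CTCAE version 3.0 grade", with no upper limit on grade. The sentence that contains the severe-event wording also lists "AEs leading to death or to discontinuation from treatment", together with serious AEs and events of interest. Section 12.5 adds that "Deaths during the treatment phase and within 30 days from the last dose of study treatment will be tabulated" by primary cause and arm.

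**The concern.** The severe-event summary by arm is one of the tables through which readers will judge the three starting doses, and AE severity is a named component of the primary endpoint (protocol 7.1, SAP 5.2). A table limited to Grades 3 and 4, combined with worst-grade counting, treats the gravest outcome perversely: when an event becomes fatal, the subject leaves the severe count for that term and the arm's rate falls.

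SAP 12.1 also allows an exact test between arms where event frequencies are judged clinically important, so per-term counts may be compared formally. Independent programming under SAP 5.3 would not reliably catch the problem, because two programmers following the same specification can agree on the same wrong table.

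**Working it through.** No sample size, error rate or event count is involved, and the plan gives no figure to reproduce. The check compares the two grade lists and then looks at what the counting rule does with the difference.

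**Step 1: grade sets.**
- Protocol 15.8, on a scale that runs from 1 to 5: {3, 4, 5}.
- SAP 12.1 as written: {3, 4, 4} = {3, 4}.
- Difference: {5}.

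**Step 2: does other SAP text restore Grade 5 to this summary?** No. Nothing in the SAP rewords this summary as Grade 3 or higher or explains a departure from the protocol.

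**Step 3: effect of the counting rule.** For one preferred term in one arm, let n3, n4 and n5 be the numbers of subjects whose worst grade is 3, 4 and 5, and let N be the number of subjects in the arm.
- Protocol rate: (n3 + n4 + n5)/N.
- SAP rate as written: (n3 + n4)/N.
- Shortfall: n5/N.

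This takes worst grade first and then restricts to the listed grades. If a program restricted first, a subject who also had a Grade 3 or 4 record of the same term would stay in. A subject whose only severe record of the term is Grade 5 is lost either way.

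**Step 4: size per subject.** Both documents plan about 35 per arm, so one such subject changes the rate by 1/35 = 2.9 percentage points. The SAP introduction reports 104 subjects enrolled. 104/3 = 34.7 per arm, and 1/34.7 is again 2.9 points.

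**Step 5: how many subjects?** This needs n5 by term and arm. Neither document gives a Grade 5 rate for any term, so the total effect cannot be derived.

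**The case against.** The strongest reply is that this is a slip of the keyboard and not a choice of analysis. Nobody deliberately lists Grade 4 twice. The repetition suggests that a third grade was meant, and 5 is the natural candidate. The SAP introduction says that the document specifies the analysis planned in the protocol, and protocol 15.8 is unambiguous. The table shells are not in the documents and may already be correct. This stands as a reason to rate the point low. It does not settle the content: a Grade 3, Grade 4 and pooled 3/4 layout is another possible intention, and it too would omit Grade 5. The protocol synopsis could seem to support that reading, since it refers to "Subject incidence rates of all AEs (including serious, Grade 3, Grade 4, treatment-related" events without naming Grade 5. Those grades are examples within all AEs tabulated by severity, so the synopsis does not override 15.8.

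The second reply is that the information is not lost. This also stands. The worst-grade summary has no ceiling, so the count at Grade 3 or higher for a term can be rebuilt from it as Grades 3 + 4 + 5. Fatal events also enter the AEs-leading-to-death and SAE summaries, the listings and the death tables. A reader might infer that fatal sepsis or fatal TLS would disappear from the safety report. The documents do not support that: the gap is confined to one summary.

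A reader might also try to size the gap from the predecessor study CC-5013-CLL-001, described in protocol 5.3.2.3. Two deaths among the first 18 patients give 2/18 = 11%, and 0.11 × 35 = 3.9 subjects per arm. The 4% in the redesigned phase who discontinued because of death gives 0.04 × 35 = 1.4. Neither figure transfers. The first 18 patients received 10 mg daily, or 25 mg on 21 of 28 days, with no escalation period. The 4% is a reason for discontinuation and not a Grade 5 rate for any preferred term. In the redesigned phase, with stepwise escalation and TLS prophylaxis, the two TLS cases among 52 patients were one Grade 2 and one laboratory TLS, so neither was a Grade 5 event.

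**Conclusion.** The point holds as a minor correction. SAP 12.1, read literally, specifies a severe-AE summary that omits Grade 5 and contradicts protocol 15.8. Under worst-grade counting, a subject whose worst grade for a term is 5 leaves that summary, at about 2.9 percentage points per subject in an arm of about 35. The number of such subjects is unknown and could be zero for any given term.

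The conclusion assumes that the table would be programmed from the SAP sentence as it stands, which cannot be confirmed without the shells. Sample size, error rates and the interim rules are unaffected. The correction is worth making because the literal text departs from the protocol on fatal events within the primary endpoint.

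**What to change.** In SAP 12.1, replace the severe-event phrase with *Grade 3 or higher (Grades 3, 4 and 5)*. Add one sentence stating that a subject whose worst grade for a term is 5 counts in the Grade 3 or higher row, and whether the grades are shown separately, pooled or both. Check the table shells and programs against the corrected text.

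The cost is one edited phrase, one added sentence and that check. No new data or analysis is needed. The SAP introduction already provides for finalization before the database lock for the PFS analysis and for a later update for OS, so there is a route for the change.

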#### **5.1.3. Safety**

Subjects will be evaluated for AEs at each visit with the National Cancer Institute Common Terminology Criteria for Adverse Events (NCI CTCAE) (Version 3.0) used as a guide for the grading of severity with the exceptions of hematological toxicities and TLS. Hematological toxicities will be graded as specified in the International Workshop on Chronic Lymphocytic Leukemia ( iwCLL) guidelines for the diagnosis and treatment of chronic lymphocytic leukemia (Hallek, 2008). Tumor lysis syndromes will be graded as specified by the Cairo-Bishop grading system.

Second primary malignancies will be monitored as events of interest and should be included as part of the assessment of adverse events (AEs) throughout the course of the study. Investigators are to report any second primary malignancies as serious adverse events (SAEs) regardless of causal relationship to study drug, occurring at any time for the duration of the study, from the time of signing the informed consent up to and including the survival follow up period. Subjects will be followed until 80% of the subjects have progressed or died or up to five years after the last subject was randomized, whichever occurs later.

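### SAP 12.1 summarises second primary malignancies as crude subject counts with no stated observation window and no person-time or competing-risk method, although they are collected through survival follow-up

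*SAP*

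**What the plan says.** **Collection.** SAP 5.1.3 makes SPMs reportable as serious adverse events whatever their cause, "from the time of signing the informed consent up to and including the survival follow up period". The follow-up rule is: "Subjects will be followed until 80% of the subjects have progressed or died or up to five years after the last subject was randomized", taking the later of the two. Protocol 8.1.7, 13.1 and Appendix 21.1 agree. The protocol's summary of changes gives the reason: whether lenalidomide raises SPM risk was unclear, and the study duration was lengthened to observe it.

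**Analysis.** SAP 12.1 contains everything planned:

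- Treatment-emergent events run from first dose "and within 30 days after the last dose of the last study drug received".
- Adverse event frequencies are tabulated "during the Treatment Phase as well as for the Follow-up Phase when appropriate".
- SPMs appear in a list of categories: "events of interest (including second primary malignancies) will be summarized separately".
- "Events of interest will also be summarized by treatment cycles".
- For counting, "a subject having the same event more than once will be counted only once and by the greatest severity".
- An exact test between arms is optional, for frequencies judged clinically important.

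Neither document mentions person-years, exposure-adjusted incidence, cumulative incidence or the competing risk of death for SPMs.

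Deaths are handled differently. SAP 12.5 commits without condition to repeating the death tables for the follow-up phase.

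**The concern.** Safety is the primary endpoint, and SPM surveillance was extended to answer a stated safety question. The planned output does not match that effort, for two reasons.

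First, the window is open. A programmer following SAP 12.1 could produce a treatment-emergent table, a table split at the end of treatment, or one count over all follow-up. The by-cycle table cannot fill the gap, because under SAP Section 9 the last cycle ends 27 days after it starts, or earlier at discontinuation or death.

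Second, a crude proportion of subjects ignores how long each was observed. Time on drug may differ by arm because starting dose is what is randomized, and survival may differ too. An on-treatment count then tends to be larger in the arm treated longer, and a whole-follow-up count tends to be larger in the arm that lives longer, even with identical SPM rates. A reader could take a difference in observation time for a difference in risk.

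**Working it through.** The plan states no SPM rate, person-time or power figure, so there is nothing to reproduce. The question is how far the choice of window and the lack of person-time could matter.

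**Inputs**

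- Horizon C = 60 months, from the five-year limb of SAP 5.1.3, used as an individual cut-off (assumption). Alternative: 60 + 60 weeks × 7/30.4 = 73.8 months, adding the accrual period in SAP 6.1.
- Tail after last dose d = 30/30.4 = 0.99 months ("within 30 days after the last dose of the last study drug received").
- Median time on drug, all assumptions for this trial: 3.1 months (the sponsor's earlier study, Protocol 5.3.2.3, starting at 2.5 mg); 5.5 months (that study's median progression-free survival, as a proxy); 12 months (a round value); 19.4 months (median progression-free survival of a single-agent study in Protocol 5.3.2.1). The last is a proxy for treatment to progression, because treatment in that study was capped at 12 months.
- Median survival 30.8 months = 14 × ln 2 / (−ln 0.73), from the other single-agent study in Protocol 5.3.2.1. The 73% is a crude proportion alive at a median follow-up of 14 months, so this is an assumption. Alternatives: 16 months (alemtuzumab study, Protocol 5.1) and 60 months (assumed).
- 35 subjects per arm (SAP 6.1).

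**Model.** Time on drug and survival are independent exponentials with rates a = ln 2/median time on drug and b = ln 2/median survival. Treatment is cut at death. Time removed by an SPM itself is ignored.

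- Mean total time at risk = (1 − e^(−bC))/b
- Mean time in window = (1 − e^(−bd))/b + e^(−bd) × (1 − e^(−(a+b)(C−d)))/(a+b)

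**Base case.** b = 0.6931/30.83 = 0.02248. Total = (1 − e^(−1.349))/0.02248 = 32.9 months, or 35 × 32.9/12 = 96 person-years per arm.

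| Median on drug (months) | Mean months in window | Share of total | Person-years in window per arm |
|---|---|---|---|
| 3.1 | 0.98 + 3.97 = 4.95 | 15% | 14 |
| 5.5 | 0.98 + 6.58 = 7.56 | 23% | 22 |
| 12 | 0.98 + 12.08 = 13.06 | 40% | 38 |
| 19.4 | 0.98 + 16.26 = 17.24 | 52% | 50 |

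**Sensitivity.** Over median survival of 16, 30.8 and 60 months and both horizons, the share is 10–21% at 3.1 months on drug, 16–31% at 5.5, 30–49% at 12 and 43–61% at 19.4. More than half the time lies outside the window unless median treatment exceeds about 13 months (median survival 16), 18–20 months (30.8) or 21–25 months (60).

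**Crude counts at equal SPM rates**

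- In-window, 5.5 against 3.1 months on drug: 22.0/14.4 = 1.5.
- In-window, 19.4 against 3.1 months: 50.3/14.4 = 3.5.
- Full follow-up, median survival 30.8 against 16 months: 32.9/21.4 = 1.5.

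The person-time rate ratio is 1.0 in all three.

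**Expected numbers.** At an assumed 3 per 100 person-years, each arm expects 0.4, 0.7 or 1.5 SPMs in the window (3.1, 5.5 or 19.4 months on drug), against 96 × 0.03 = 2.9 over full follow-up. At 1 and 5 per 100 the full follow-up figures are about 1.0 and 4.8. Three events in 96 person-years give 3.1 per 100. The exact 95% limits for three events are χ²(0.025; 6)/2 = 0.62 and χ²(0.975; 8)/2 = 8.77, that is 0.6 to 9.1 per 100 person-years.

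**The case against.** A reader might infer that the SAP confines SPMs to the 30-day window. It does not. The limit defines treatment-emergent events, while the SPM summary is a separate item with no window. Read with SAP 5.1.3, the conditional Follow-up Phase table is a natural place for late SPMs. The fault is an unstated window and estimator, not an exclusion.

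A reader might also infer that most at-risk time lies outside that window. That depends on the scenario. It holds at 3.1 and 5.5 months on drug, but in the base case 52% lies inside at 19.4 months. Nor do the documents establish that SPMs occur late, and the calculation does not assume it.

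It would likewise be too strong to say the arms are formally compared on crude counts. The exact test is optional, the rest is descriptive, and subject listings are planned. No passage shows that survival or time on drug does differ between arms.

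Finally, about three events per arm will not support precise inference, and SAP Section 3 foresees an update for the survival analyses, when SPM reporting could be added. Both points stand. The first limits what the analysis can show, but a rate with its interval makes that imprecision visible and a bare count hides it. The second is an opportunity, not a commitment, since the SAP does not say SPMs would be included.

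**Conclusion.** The concern holds in a limited form. SPMs are followed through survival follow-up, yet SAP 12.1 provides only crude by-subject frequencies with no stated window, a by-cycle table and conditional follow-up tables. Neither document offers a person-time or competing-risk method.

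The size is illustrative. With median survival of 30.8 months and a 60-month horizon, the 30-day window would hold 15% to 52% of at-risk time, and arms with equal SPM rates could show expected in-window counts differing by a factor of 1.5 to 3.5. These figures rest on independent exponential times and on durations borrowed from other studies. Correlation between time on drug and survival would change them. The 3.5 sets the two extreme treatment durations against each other and is not a forecast for this trial.

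The documents do not support saying that late SPMs are excluded or that most of the risk period is lost. This is a worthwhile, inexpensive improvement to the plan, and its results will be descriptive.

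**What to change.** Add a paragraph to SAP 12.1 stating that:

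- SPMs are analysed in all dosed subjects from first dose to last contact or death, irrespective of the 30-day rule.
- Subjects with a first SPM are reported per 100 person-years by arm with exact 95% confidence intervals, with person-time ending at the first SPM, death or last contact.
- Cumulative incidence by arm is estimated with death as a competing event.
- The treatment-emergent count is shown as a labelled subset.
- The results are descriptive.

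The required dates (first dose, SPM, death and last contact) are already collected. The cost is one paragraph, one extra table and one figure. The downside is limited to that work and to wide intervals with about 35 subjects per arm.
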